10.1.3 Correlative objectives

To evaluate the predictive capacity of circulating analytes within both genetic cohorts circulating tumor DNA sequencing/quantification, circulating tumor cell number, circulating tumor cell composite gene expression by pooled RT-PCR will be measured. Continuous biomarkers will be described using means and standard deviations or medians with percentile. Categorical covariates will be described with counts and frequencies.

- The association of correlative biomarkers with response will be assessed using logistic models with response as outcome and the correlative covariates as the independent predictors. The association of correlative biomarkers with failure will be assessed using Cox models with response rate as the outcome and correlative covariates as the independent predictors
- Correlations between the metastatic biopsy and circulating analysis will be compared and the proportion of matches will be reported. McNemar's test may be used.
- Correlations of liquid assays and tissue-based analyses will be reported using Pearson or Spearman correlation coefficients as is appropriate.

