10. STATISTICAL METHODS AND SAMPLE SIZE DETERMINATION

10.1 Study Endpoints

10.1.1 Analysis of the primary endpoint

The primary endpoint of the study is the response rate of the DRPro cohort. Response is defined as achieving a complete response (CR) or partial response (PR) by either radiographic response according to RECIST v 1.1 or PSA response. The count of responses and corresponding response rate with the 95% binomial confidence interval will be reported in the DRPro patients.

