10.1.2 Analysis of the secondary endpoints

- The response rate and 95% binomial confidence interval will be reported for DRDef patients.

The following endpoints will be reported for DRDef and DRPro patients separately

- Objective progression-free survival (combined radiographic and clinical progression-free survival) will be reported using Kaplan-Meier methods. This is measured from the date of treatment arm assignment until the specified tumor progression (assigned at the earliest observed time). Patients whose disease has not progressed at follow-up will be censored at the date when the last tumor assessment determined a lack of progression.
- Objective radiographic disease response rate is determined by the proportion of patients with measurable disease that have a response (CR+PR) according to RECIST v1.1. The proportion of responders will be reported with the corresponding 95% binomial confidence interval.
- PSA progression-free survival (PSA-PFS) will be reported as the composite of survival and duration of PSA control as defined by after a start of therapy from baseline to time of first PSA increase $\geq 25\%$ and ≥ 2 ng/mL above the nadir and confirmed by a second value at or beyond 4 weeks later. Kaplan-Meier methods will be used to report PSA-PFS.

- PSA response rate (≤ 0.2 ng/ml, 50% decline, 90% decline) proportions will be reported with corresponding 95% binomial confidence intervals. A waterfall plot of the best PSA response decline will be reported.
- Evaluate the qualitative and quantitative AE summaries will be reported by DNA repair status and organized by body system, frequency of occurrence, intensity (e.g. severity grade) and causality or attribution. Counts and proportions will be included. Treatment exposure will be summarized for all patients, including dose administration, number of cycles, dose modifications or delays and duration of therapy. Categorical variables will be reported using counts and frequencies. Continuous variables will be summarized using means or medians with the appropriate measure of variability.
- Duration of combined radiographic and PSA response will be reported using Kaplan-Meier methods.

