10.2 Analysis Populations

10.2.1 Response-to-treatment populations

All patients who meet eligibility criteria and receive at least one dose of study medication will be included in the main analysis of the response rate, even if there are major protocol deviations (e.g., incorrect treatment schedule or drug administration). Each patient will be assigned to one of the following categories for each response outcome:

TABLE 7: Categories for Response to Treatment

Category	Response
1	Complete response
2	Partial response
3	Stable disease
4	Progressive disease
5	Early death from malignant disease
6	Early death from toxicity
7	Early death from other causes

8	Unknown (not assessable/insufficient data)
---	--

NOTE: By arbitrary convention, category 8 designates unknown status in a clinical database. Patients in response categories 4 to 8 will be considered to have treatment failure (disease progression)

Conclusions are to be based on the population of all eligible patients who receive at least one dose of study medication. Subanalyses will be performed on various subsets of patients, such as those with no major protocol deviations, those who have at least one measure of response after starting treatment or those who continued in the study for the entire treatment period (i.e. did not withdraw prematurely). Sub-analysis will not serve as the basis for drawing conclusions concerning treatment's efficacy.

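### Section 10.1.3 gives response rate as the outcome of the Cox models meant to relate biomarkers to failure; it should name a time-to-failure endpoint

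*Combined protocol and SAP*

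**What the plan says.** Section 10.1.3 contains two modelling sentences. The first deals with response: "The association of correlative biomarkers with response will be assessed using logistic models with response as outcome". The second deals with failure, whose association with the biomarkers is to be assessed by "Cox models with response rate as the outcome and correlative covariates as the independent predictors".

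The terms used there are defined elsewhere in Section 10:

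- **Response** (10.1.1): "Response is defined as achieving a complete response (CR) or partial response (PR) by either radiographic response according to RECIST" v1.1, or by PSA response. It is summarised as a proportion: "The count of responses and corresponding response rate with the 95% binomial confidence interval will be reported in the DRPro patients".
- **Failure** (10.2.1, note to Table 7): "Patients in response categories 4 to 8 will be considered to have treatment failure (disease progression").
- **Time-to-event endpoints** (10.1.2): "Objective progression-free survival (combined radiographic and clinical progression-free survival) will be reported using Kaplan-Meier methods", with the censoring rule "Patients whose disease has not progressed at follow-up will be censored at the date when the last tumor assessment determined a lack of progression". PSA-PFS and duration of combined response are also reported by Kaplan-Meier.

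Section 10.1.3 does not link the Cox models to any of these time-to-event endpoints, and no other section corrects the sentence. Section 1.2.4 describes the correlative studies as exploratory only.

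**The concern.** A Cox model needs an event, a time origin, an event time for those who have the event, and a censoring rule for those who do not. Response rate, as Section 10.1.1 uses it, supplies none of the timing. The sentence also disagrees with itself: its aim is failure and its outcome is response, which the sentence before it has already assigned to logistic models.

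This is the only planned model linking the circulating analytes to failure, and evaluating the predictive capacity of those analytes is the only exploratory objective in Section 2.4. If the outcome stays unnamed, the analyst must choose among several time-to-event endpoints after the data are in. If the sentence is followed literally, the result would be labelled an association with failure when it is not one.

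**Working it through.** The plan gives no event count, hazard ratio or power for the Cox analysis, so there is no figure to reproduce. The check compares definitions and then counts events.

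**1. Does the stated outcome suit the model?** Response is a yes/no status per patient, and response rate is the proportion of patients with that status, given with a binomial interval. Section 10.1.1 sets no origin, event time or censoring rule for it.

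**2. Does the stated outcome measure failure?** Table 7 has eight categories:

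| Table 7 category | Response | Treatment failure |
|---|---|---|
| 1–2 (CR, PR) | yes | no |
| 3 (stable disease) | no | no |
| 4–8 (progression, early death, unknown) | no | yes |

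Category 3 is in neither group, so failure is not the complement of response. The Table 7 definition of failure is also a category without a date.

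**3. How many events would a response-based Cox model have?** This takes response as the event, a reading the plan does not state. Expected events = cohort size × response rate, using the cohort sizes and design rates in Section 10.3.6.

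| Cohort | At the null rate | At the alternative rate |
|---|---|---|
| DRPro, 35 patients | 35 × 0.06 = 2.1 | 35 × 0.20 = 7.0 |
| DRDef, 12 patients | 12 × 0.45 = 5.4 | 12 × 0.70 = 8.4 |

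That is about 2 to 7 events in DRPro and about 5 to 8 in DRDef.

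**4. What would such a model return?** An illustrative simulation used 4,000 patients. All its parameters are assumptions: a log hazard ratio for failure of 0.50 per SD of the biomarker, a log odds ratio for response of −0.5 per SD, and response near 20%.

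| Cox outcome | Estimated log hazard ratio per SD |
|---|---|
| Failure time | 0.499 |
| Response as event, constant time | −0.397 |
| Response as event, on the failure-time scale | −0.015 |

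Only the first recovers the failure effect. The other two give different answers from each other, depending on how time is filled in.

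**5. Can a PFS endpoint be substituted directly?** Nearly, but the definitions of objective PFS differ:

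| Place | Origin | Death an event? |
|---|---|---|
| Synopsis and 2.2 | start of treatment | yes |
| 7.6.7.6 | assignment to treatment arm | yes |
| 10.1.2 | assignment to treatment arm | not mentioned; tumor progression only |

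**The case against.** The best defence is that this is a drafting slip with little at stake. The sentence says failure and Cox, and Section 10.1.2 has just listed time-to-event endpoints, so the word response was probably carried over from the logistic sentence. The analysis is exploratory, and no primary or secondary endpoint, stopping rule or go/no-go decision uses it. All of this stands, and it limits the weight of the point. It does not remove it: the general intent can be recovered but the endpoint cannot, because Section 10.1.2 offers three Kaplan-Meier endpoints, one of which (duration of response) applies to responders only.

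A reader might also infer more than the documents support:

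- *That the model cannot be fitted.* Software will return an estimate once someone supplies times, as the simulation shows. The defect is that the plan gives no event time and the outcome is not failure.
- *That the hazard ratio would be the reverse of the one for failure.* Stable disease is neither response nor failure, so the two are not mirror images. One simulated version came out near zero, not reversed.
- *That most patients would have a PFS event, so that PFS would supply far more events.* The documents give no PFS rate, median or event count. Follow-up after removal from treatment is 30 days (Section 5.6.2), and patients without progression are censored at the last tumor assessment, so a high event fraction cannot be assumed.

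**Conclusion.** The point holds as a specification error in a stated analysis. The named outcome has no event time or censoring rule and does not measure what the sentence sets out to assess. A Cox model on response would estimate something else, from about 2 to 7 events in DRPro and about 5 to 8 in DRDef. Those counts assume full cohorts of 35 and 12, true rates within the design ranges, and response taken as the event. The simulation rests entirely on assumed parameters and only illustrates the mismatch.

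The consequence is confined to the exploratory correlative objective. A reader should not extend it to the primary endpoint, the sample size or the Simon decision rules, none of which depends on this model. That objective PFS was intended is a reasonable inference, but the documents do not say so, and the sponsor should confirm it.

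**What to change.** In Section 10.1.3, replace response rate as the Cox outcome with a time-to-failure endpoint the plan already defines. Objective PFS is the natural choice, with PSA-PFS added if the sponsor intends it. Leave the logistic models for response as they are.

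In the same edit:

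- use one time origin for objective PFS in the synopsis and Sections 2.2, 7.6.7.6 and 10.1.2;
- state in Section 10.1.2 that death counts as an event, in line with the other three places.

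The cost is a few words in Section 10.1.3 and matching edits to the PFS definitions. No new data, patients or assessments are needed.

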ID: UMCC 2018.108

NCT03787680

**Targeting Resistant Prostate Cancer With ATR
and PARP Inhibition (TRAP Trial)**

Drug Substance	AZD6738
Study Number	UMCC 2018.108
Version Number	4.1
Date	27JUN2023

A Multi-Center Phase II Study Testing the Activity of Olaparib and AZD6738 (ATR Inhibitor) in Metastatic Castration-Resistant Prostate Cancer.

Short Title: Targeting Resistant prostate cancer with ATR and PARP inhibition (TRAP trial)

PROTOCOL SYNOPSIS

A Multi-Center Phase II Study Testing the Activity of Olaparib and AZD6738 (ATR Inhibitor) in Metastatic Castration-Resistant Prostate Cancer.

Principal Investigator/Sponsor-Investigator

[name]., Ph.D.

University of Michigan, Department of Medical Oncology
[name]
[name]
[contact]
[contact]
Email: [contact]

IND: 141954

Coordinating Center: University of Michigan

Biostatistician

[name]
University of Michigan
[name]
[name]
[name]
[contact]
Email: [contact]

Study site(s) and number of subjects planned

The study will enroll 47 evaluable patients from 4 academic centers.

Study period	Phase of development
Estimated date of first subject enrolled	1/2019
Estimated date of last subject completed	4/2021

Study design

This is a phase II Simon 2-stage study evaluating the response rate for the combination of AZD6738 (ceralasertib) and olaparib for patients with metastatic castration-resistant prostate cancer (mCRPC) who are DNA repair proficient (DRPro) and deficient (DRDef). Patients are DRDef based on somatic mono- or bi-allelic loss of ATM, somatic biallelic loss of either BRCA1 or BRCA2 OR known mono- or biallelic germline loss in ATM, BRCA1 or BRCA2.

Objectives

Primary Objectives:	Outcome Measures:
To determine the response rate of the combination of olaparib and AZD6738 in mCRPC patients who are DNA repair proficient (DRPro, e.g. intact ATM, BRCA1 and BRCA2).	The rate of response (CR/PR) per radiographic response according to RECIST v1.1 or PSA ($\geq 50\%$ decline) in DRPro patients.

Secondary Objective:	Outcome Measure:

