Patients with progressive, metastatic, castration-resistant prostate cancer who received a) at least one line of systemic therapy for mCRPC or b) failed ongoing second generation anti-hormonal therapy (e.g. abiraterone) in the hormone-sensitive or non-metastatic castration resistant phases of disease. They must remain on continuous LHRH agonist/antagonist, unless they have undergone orchietomy.

Duration of treatment

Patients must have washed out of any prior systemic therapy for either 3 weeks or 5 half-lives (whichever is longest), excluding prednisone, LHRH agonist/antagonists, bisphosphonate or RANKL inhibitor. The median duration of study per patient is estimated to be approximately 12 months.

Investigational product, dosage and mode of administration

Olaparib, 300 mg by mouth, twice a day, days 1-28 of a 28-day cycle.
AZD6738, 160 mg by mouth, daily, days 1-7 of a 28-day cycle.

Statistical methods

For the DRPro population (characterized through study sequencing or previously completed), using an Optimal Simon 2-stage design, this cohort will be 35 total patients with an interim for futility after 17 DRPro patients have been accrued. If 2 or more responses are seen in the first stage, then the second stage will open and accrue 18 more DRPro patients. If 5 or more patient responses are seen out of the 35 DRPro patients, then the combination treatment will be deemed interesting for further study in a DRPro population. The null response rate from the

TOPARP-A study is 6%. The current design will detect at 80% power, a response rate of 20% or greater with 5% one-sided type I error.

For the DRDef population (characterized through study sequencing or previously completed), using a Mini-Max Simon 2-stage design. A set of 12 DRDef will be treated and if 6 or more responses are seen, this would support consideration to expand (with amendment or new protocol) with another 13 patients or a completely separate trial.

Principal analyses will report the response rate (CR/PR) per radiographic response according to RECIST v1.1 or PSA ($\geq 50\%$ decline) in DRPro and DRDef patients. The cohorts will be separated for all efficacy analyses.

TABLE OF CONTENTS		PAGE
	TITLE PAGE	1
	TABLE OF CONTENTS	6
	LIST OF ABBREVIATIONS AND DEFINITION OF TERMS	11
1.	INTRODUCTION.....	14
1.1	Background.....	14
	1.1.1 Pre-clinical experience.....	15
	1.1.2 Toxicology and safety pharmacology summary	15
	1.1.3 Clinical experience.....	16
1.2	Research Hypothesis	16

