1.2.4 Rationale for circulating correlative studies

Circulating tumor DNA (ctDNA) and circulating tumor cells (CTCs) are unique biologic samples as they attempt to recapitulate the tumor heterogeneity into a single blood draw. These liquid biopsy approaches provide an opportunity to develop blood-based predictive or prognostic biomarkers that could obviate the need for tumor-directed biopsies. By combining ctDNA with both morphologic and possible DNA/RNA-based analyses of CTCs, the mutational and transcriptional tumor landscape may be determined. Furthermore, evaluating the concordance of a serum sample to the metastatic biopsy will allow for both: validation of the liquid-based approach and likely identification of patients harboring DNA repair defects that are not present in the single metastatic site biopsied. These analyses will be collected prior to treatment in order to develop these assays as predictive biomarkers of response and during treatment to monitor alterations in circulating disease. CTC and ctDNA analyses will also be done at the end of treatment to explore mechanisms of resistance. These correlative studies are exploratory in nature only.

The ctDNA and CTC analyses to correlate with response to treatment and clinical characteristics of disease, will be done for all patients enrolled into treatment. DNA modifications of these samples (e.g., epigenetic or otherwise) and noncoding elements (e.g., telomere length, introns) may be investigated with the above goals in the future as excess tissue and blood specimens will be banked. Correlation of these tumor characteristics can also be compared retrospectively to each patient's clinical course. Published algorithms of the above data for olaparib response will be validated and new ones created/tested.

Previous tissue obtained either in routine care OR left over when the on-study biopsy was performed may be requested. This will be labeled by study ID only and may be utilized by the coordinating center or shared with sponsor. If samples are shared with sponsor, they will NOT be utilized for next generation sequencing analyses to avoid genetic privacy concerns. Patients may opt-out of the request for prior tissue and/or sharing of prior/study tissue with sponsor. Left over tissue from the biopsy will be sent to coordinating center (after sequencing completed at TEMPUS).

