10.3.6 Sample size calculation

The statistical design for DRPro will be an Optimal Simon 2-stage Phase II. Based on the TOPARP-A study the null response rate for DRPro is 6% and a response rate of 6% or less would not be interesting. Accrual of 35 DRPro patients will provide 80% power to detect a response rate of 20% or greater with 5% type I error. Stage 1 will accrue 17 DRPro patients. If 1 or less DRPro patients have a preliminary response (CR/PR using radiographic by RECIST v.1.1 or PSA decline $\geq 50\%$) then the DRPro cohort will stop. If 2 or more responses occur, then the 2nd stage will begin and another 18 DRPro patients will be accrued. If 5 or more patient responses are seen out of the 35 DRPro patients, then the combination treatment will be deemed interesting for further study in the DRPro population.

The statistical design for the DRDef is a Mini-Max Simon 2-stage Phase II. Based on a response rate of 45% within the first 12 weeks in TOPARP-A, a response rate of under 45% would not be interesting. Stage 1 of this design requires 12 DRDef patients and if 5 or less patients have a preliminary response (CR/PR using radiographic by RECIST v.1.1. or PSA decline $\geq 50\%$), then the DRDef cohort would not be of interest. If 6 or more patients do respond, this would support consideration to expand (with amendment or new protocol) with another 13 patients (to a total of 25 patients) or a completely separate trial. Accrual of 25 patients would provide 80% power to detect a response rate of 70% or greater with 5% type I error. If 16 or more patient responses were seen in a 25 total DRDef patient cohort, then the combination treatment would be deemed interesting for further study DRDef. Different RR are used for DRDef and DRPro as different expected baseline RR.

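### The planned tissue-to-blood comparison does not define a match, and none of its statistics estimates how many tissue-DRDef patients the blood assay detects

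*Combined protocol and SAP*

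**What the plan says.** Section 10.1.3 (Correlative objectives) plans three things for tissue against blood:

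- A match proportion: "Correlations between the metastatic biopsy and circulating analysis will be compared and the proportion of matches will be reported".
- McNemar's test, worded as an option and not as a commitment.
- Pearson or Spearman coefficients between liquid and tissue assays.

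The section does not say whether a match is a patient-level DRDef/DRPro call or agreement on individual alterations, or which patients enter the comparison. It names no positive or negative agreement, sensitivity or specificity. It gives no confidence interval for the match proportion, although sections 10.1.1 and 10.1.2 attach 95% binomial intervals to the response proportions.

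Section 1.2.4 states what the comparison is for: "validation of the liquid-based approach and likely identification of patients harboring DNA repair defects that are not present in the single metastatic site biopsied". The same section labels the correlative work exploratory.

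**The concern.** Each aim in section 1.2.4 concerns one direction of disagreement. Validation asks what share of tissue-DRDef patients is also positive in blood. The second aim asks which tissue-negative patients are positive in blood. A single match proportion adds the two kinds of agreement together, and with a DRPro majority most of it comes from negative-negative pairs. McNemar's test asks only whether the two methods call the same share of patients positive, so opposite errors cancel. A correlation coefficient summarizes association and gives no detection rate.

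At stake is how the liquid-assay result can be read. A match figure of about three quarters, or a non-significant McNemar result, could accompany good or very poor detection, and the planned output would not tell the reader which.

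**Working it through.** **Inputs from the documents.** The synopsis gives the total ("The study will enroll 47 evaluable patients from 4 academic centers"), the DRPro cohort ("this cohort will be 35 total patients with an interim for futility after 17 DRPro patients have been accrued") and the DRDef cohort ("A set of 12 DRDef will be treated and if 6 or more responses are seen"). The plan's total reproduces: 35 + 12 = 47. The documents give no figure for the concordance analysis itself.

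**Assumptions, not in the documents.** A match is a patient-level DRDef/DRPro call; all 47 patients have both results; tissue status equals cohort.

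**Notation.** a = positive in both; b = tissue-positive, blood-negative; c = tissue-negative, blood-positive; d = negative in both.

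- Match proportion = (a + d)/(a + b + c + d)
- Positive percent agreement (PPA) = a/(a + b)
- Negative percent agreement (NPA) = d/(c + d)
- Exact two-sided McNemar p = min(1, 2 × P[Bin(b + c, 0.5) ≤ min(b, c)])
- For binary calls the Pearson or Spearman coefficient is phi = (ad − bc)/√[(a+b)(c+d)(a+c)(b+d)]
- Intervals are Clopper-Pearson 95%

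**Always-negative assay.** a = 0, b = 12, c = 0, d = 35. Match = 35/47 = 74.5%. PPA = 0/12 = 0%.

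**Same match, different assays.** With 47 pairs the match is 35/47 whenever b + c = 12, however the 12 disagreements are split:

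| a, b, c, d | Match | PPA (95% CI) | NPA (95% CI) | McNemar p | phi |
|---|---|---|---|---|---|
| 0, 12, 0, 35 | 74.5% | 0% (0-26.5) | 100% (90-100) | 0.0005 | undefined |
| 6, 6, 6, 29 | 74.5% | 50% (21-79) | 82.9% (66-93) | 1.0 | 0.33 |
| 9, 3, 9, 26 | 74.5% | 75% (43-95) | 74.3% (57-88) | 0.15 | 0.44 |
| 12, 0, 12, 23 | 74.5% | 100% (73.5-100) | 65.7% (48-81) | 0.0005 | 0.57 |

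**What McNemar's test adds.** For the always-negative assay, p = 2 × 0.5^12 = 0.0005, so the test would flag it. It gives the same p in the last row, where every tissue-DRDef patient is detected. With 6 against 6 discordant pairs p = 1.0 at 50% detection. With 9 against 9 (a = 3, d = 26) p is again 1.0, at 3/12 = 25% detection and a match of 29/47 = 61.7%.

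**What the coefficient adds.** Phi does differ between the rows, but it cannot be computed for the always-negative assay and does not convert to a detection rate.

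**Range for the always-negative match.** The number of paired patients is unknown. For an assumed 20-35 DRPro and 4-12 DRDef pairs, the lowest value is 20/(20 + 12) = 62.5% and the highest is 35/(35 + 4) = 89.7%. At the DRDef prevalence of about 20% given in section 1.1 it would be 80%.

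**Who has a tissue result.** Under sections 1.2 and 3.3.2, a patient whose biopsy failed or was unsafe and who has ctDNA testing is designated DRPro by rule. A patient with known germline loss needs no new biopsy. Cohort label is therefore not the same as tissue status. Taking it as such would count some patients without tissue as tissue-negative, and some DRDef patients may have no tissue result either.

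**The case against.** The strongest reply has four parts.

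First, the plan holds more than the match proportion. A reader might infer that an always-negative assay would pass unnoticed. The documents do not support that: if the optional McNemar test is run, it rejects that assay clearly. The always-negative example counts only against the match proportion; the balanced-error table is the one that counts against McNemar's test. This stands.

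Second, a match need not be a patient-level call. If matches were counted per alteration found in tissue, an always-negative assay would score near zero. Section 10.1.3 also frames its aim within both genetic cohorts, and match rates reported by cohort would approximate positive and negative agreement. This stands as a limit on the 74.5%. It does not remove the point, because the text commits to neither reading.

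Third, a reader might infer that a non-significant McNemar result will be taken as validation, or that the plan conceals tissue-negative, blood-positive patients. No sentence says the former, and that group is one of the two discordant cells from which the test is computed. What remains is that the plan does not commit to reporting those patients.

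Fourth, little depends on the result. The work is exploratory, section 1.2 bars any ctDNA assay from assigning DNA repair status, and sample collection may lapse when the laboratory is unavailable (study calendar, footnote n). With at most 12 DRDef patients, better statistics could not firmly validate the assay either. All of this stands and sets the severity. It does not make the planned statistics answer the stated question.

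**Conclusion.** The point holds in a limited form. Section 10.1.3 leaves a match undefined and names no statistic that estimates detection of tissue-DRDef patients, although section 1.2.4 makes validation and discovery of missed defects the purpose.

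The 74.5% is conditional on all three assumptions listed with the calculation; when only the number of pairs varies, the 62.5-89.7% range applies. The structural result is firmer: for patient-level calls, one match value is compatible with any detection rate from 0% to 100%, and a McNemar p of 1.0 is compatible with 25% or 50% detection. A non-significant McNemar result is therefore not evidence of agreement.

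A reader might go further and infer that cohort assignment or the primary response analysis is affected. It is not. Severity is low: this is a free improvement to an exploratory analysis.

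**What to change.** Amend section 10.1.3 as follows:

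- Define a match as agreement on the patient-level DRDef/DRPro call.
- Restrict the comparison to patients with an actual tissue sequencing result and a blood result, so that patients designated DRPro without tissue are not counted as tissue-negative. State the number of pairs.
- Report positive and negative percent agreement, each with an exact 95% confidence interval. The match proportion may stay as a supplement.
- List tissue-negative, blood-positive patients individually and call them discordant. The term false positive would be wrong, because section 1.2.4 expects blood to show defects that the single biopsied site lacks, so tissue is an imperfect reference.
- State that McNemar's test, if run, compares positive rates and is not evidence of agreement.

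The cost is wording only: no new samples, assays or patients. The downside is wide intervals, since the protocol plans at most 12 DRDef patients and some may lack tissue; 6 of 12 detected gives 21-79%. That width shows how little the comparison can establish.
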